**Table 2-3: Procedural Outline after the Treatment Period (CA209812) - Follow Up**

Procedure	X, Follow-Up, Visits 1 and 2 a	Notes
Efficacy Assessments		
B Symptoms	X	To be collected only at Follow-up Visit 1
Radiographic Assessments		
FDG-PET CT or FDG MRI scan from vertex to toes b	See note	For participants who discontinue study treatment prior to disease progression, no further FDG-PET CT or PET MRI will be obtained.
Participant Status		
Survival Status	X	Survival follow-up will stop after safety Follow-up Visit 2.

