**Table 2-3: Procedural Outline after the Treatment Period (CA209812) - Follow Up**

Procedure	X, Follow-Up, Visits 1 and 2 a	Notes
Subsequent anti-lymphoma therapies	X	It can be accomplished by visit or phone contact to assess subsequent anti-cancer therapy. Per Revised Protocol 01, stop after safety Follow-up Visit 2.
Post-nivolumab stem cell transplant follow-up (if applicable)	X	Completion of associated eCRF page. Per Revised Protocol 01, stop after safety Follow-up Visit 2.
GVHD Assessments	X	Only for participants who discontinued study therapy by proceeding to allogeneic SCT. See Section 9 and Appendix 9 . Per Revised Protocol 01, stop after safety Follow-up Visit 2.

a X, Follow-up visit 01 occurs 35 days ± 7 days from last dose and Follow-up visit 02 occurs 100 days ± 7 days from the last dose.

b Should a participant have a contraindication for CT IV contrast, a non-contrast CT of the chest and a contrast enhanced MRI of the abdomen and pelvis may be obtained. CTs and MRIs should be acquired with a slice thickness of 5 mm or less with no gap (contiguous).

[figure not shown]

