### **3.2 Background**

[figure not shown]
High-dose chemotherapy with ASCT remains the optimal option to achieve a durable remission in patients with HL who have relapsed or are refractory to the standard frontline combination chemotherapy. Furthermore with ASCT approximately 50% of the patients are cured. Unfortunately, the remaining 50% of ASCT patients do not experience long-term disease control with median overall survival of approximately 27 months. In particular, the prognosis remains exceedingly poor for patients who experience relapse or progressive HL within one year after ASCT where the median survival time is approximately 1.2 years. Several small clinical studies

have examined various agents in the ASCT relapsed HL population with uniformly poor results. Therefore, the therapeutic options for these patients remain very limited. This underscores the need for more effective regimens for the treatment of relapsed, refractory HL.

Brentuximab vedotin is approved for patients who have progressed after ASCT or after failure of at least two prior multi-agent chemotherapy regimens in patients who are not ASCT candidates. In a pivotal phase 2 study of 102 patients with relapsed or refractory HL following ASCT, treatment with BV 1.8 mg/kg every 3 weeks resulted in an objective response rate (ORR) of 75% (95% CI: 64.9, 82.6). The CR rate was 34% (95% CI: 25.2, 44.4) and the median progression-free survival (PFS) for all patients on study was 5.6 months (95% CI: 5.0, 9.0). Longer follow up showed that the median overall survival (OS) and median PFS were 40.5 months (95% CI: 28.7, 61.9) and 9.3 months (95% CI: 7.1, 12.2), respectively. The estimated 5-year OS and PFS rates were 41% (95% CI: 31, 51) and 22% (95% CI: 13, 31), respectively. It should also be noted that BV is effective at the time of retreatment. Brentuximab vedotin is currently being developed by Seattle Genetics for the treatment of hematological malignancies.

Nivolumab has demonstrated promising activity as single agent in relapsed HL.

[REDACTED]

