#### 4 OBJECTIVES AND ENDPOINTS

**Table 4-1: Objectives and Endpoints**

Objectives	Endpoints

Primary
 
 
To compare progression free survival of nivolumab + BV vs BV per investigator assessment.
 
	
 
Progression Free Survival (PFS): defined as time from date of randomization to death, or disease progression.
 

Secondary
 
 
To compare the complete response rate of nivolumab + BV vs BV per investigator assessment.
 
To assess objective response rate and duration of response per investigator assessment.
 
To assess duration of complete response per investigator assessment.
 
To assess overall survival of participants treated with nivolumab + BV vs BV.
 
	
 
Complete Response Rate (CRR): defined as proportion of participants who have achieved complete response (Lugano 2014 classification)
 
Objective Response Rate (ORR): defined as the proportion of participants who have achieved complete response or partial response (Lugano 2014 classification)
 
Duration of response or duration of complete response (DOR or DOCR): defined as the time from first response or complete response to the date of initial objectively documented progression as determined using the 2014 Lugano classification or death due to any cause
 
Overall Survival (OS): defined as the time between the date of randomization and the date of death.
 

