- Duration of study participation: Randomization is within 28 days of the screening. The recruitment period is approximately 34 months with a follow up of 4 years after the last patient first visit (LPFV). Participants will receive active treatment of nivolumab until progression or unacceptable toxicity plus BV for 16 cycles or until progression or unacceptable toxicity, whichever comes first, or BV alone up to 16 cycles, or until progression or unacceptable toxicity, whichever occurs first. The treatment period will be followed by a survival follow up period.

As of 17- Oct- 2019, enrollment in this study was stopped at the decision of the Sponsor. For currently enrolled participants, at the investigator's discretion, the same study treatment can be continued if the participant is considered to have clinical benefit. Assessments of efficacy and safety will continue per protocol; however, efficacy assessments will be done by investigator. [REDACTED]

[REDACTED] For participants who continue the study treatment, BMS will continue to provide study drugs, per country requirements, until the participant meets the protocol discontinuation criteria. Participants who discontinue all study drugs will continue safety follow-up per protocol requirements. Survival follow-up will stop at safety Follow-up Visit 2 as presented in [Table 2-3](#).

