Secondary	
CRR/CMR based on investigator assessment will be compared in two randomized arms via a two-sided, Cochran-Mantel-Haenszel test stratified by the same factors used in randomization. An estimate of the treatment odds ratio between the nivolumab + BV and BV arm along with corresponding two-sided 95% CIs and p-value will be presented. The estimate of the CRR/CMR and associated exact two-sided 95% CIs (by Clopper - Pearson method) will be presented for both arms.
 
ORR as defined as proportion of participants who achieved CR/CMR or PR/PMR before taking any subsequent anti-cancer therapy, will be computed in each treatment group along with the exact 95% CI using Clopper-Pearson method.
 
Duration of response (or complete response) in each treatment group will be estimated using KM product-limit method for participants who achieve PR or CR /CMR (or CR/CMR only). Median values along with two-sided 95% CI will be calculated.
 
The OS curves for each treatment group will be estimated using the Kaplan-Meier product-limit method. Two-sided, 95% confidence intervals for median OS will be provided. For participants without documentation of death, OS will be censored on the last date the participant was known to be alive. When the primary endpoint, PFS, is statistically significant, the secondary endpoint CRR/CMR will be tested. The hierarchical testing procedure that ensures the study-wise type I error is controlled at 5% levels will be described in the SAP.

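### Overall survival by arm is kept although survival follow-up now ends about 100 days after last dose, so OS is truncated, censored in step with progression and arm, and cannot be answered as planned

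*Protocol*

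**What the plan says.** **Stop rule.** Protocol Table 2-3 states "Survival follow-up will stop after safety Follow-up Visit 2", and its footnote adds "Follow-up visit 02 occurs 100 days ± 7 days from the last dose". Section 5.3 ends the trial at the same visit.

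**OS objective.** Table 4-1 keeps the secondary objective "To assess overall survival of participants treated with nivolumab + BV vs BV". Section 10.3.1 still plans the estimate by arm: "The OS curves for each treatment group will be estimated using the Kaplan-Meier product-limit method". It asks for an interval around the median as well, and it sets this censoring rule: "For participants without documentation of death, OS will be censored on the last date the participant was known to be alive".

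**Treatment duration.** Section 8.1 makes progression a mandatory reason to stop treatment. Under Section 7.1, BV stops after at most 16 cycles. Nivolumab runs to progression or unacceptable toxicity, with an optional stop in complete response after 2 years.

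**Limits on analysis.** Section 10 rules out formal testing and inference. It makes the previously planned analyses conditional on being appropriate and refers to the SAP for detail.

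**SAP.** The version supplied is 1.0 of 24-Feb-17, which predates the revision. Section 1 still foresees up to 4 years of survival follow-up. Section 7.5.2.3 plans a stratified OS log-rank test, a Cox hazard ratio and optional survival rates at 6 to 36 months.

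**Leftover text.** The protocol synopsis (Overall Design) and Section 5.1 still describe following participants for progression and then survival. Section 5.1 and SAP Section 2.1 still give 4 years of follow-up after the last patient's first visit.

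**The concern.** Kaplan-Meier estimation assumes that a participant censored at a given time has the same later risk of death as those still being followed. Here the censoring time is set by the last dose, and the last dose is often set by progression. Participants who progress leave the OS risk set about 100 days later. Those who remain are mostly on treatment or recently off it. If death is more likely after progression, the curve is too high.

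The window also depends on arm. BV alone has a fixed cap; the combination does not. Even two arms with identical survival would be observed over different lengths of time.

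At stake is whether the report will carry an OS curve, a median and an implied comparison that the retained data cannot support.

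**Working it through.** The plan gives no OS event count, power or precision, so there is no OS figure of its own to reproduce.

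**1. Length of the OS window**

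Inputs: 21-day cycles (Section 5.1), 16 BV cycles (Section 7.1), Visit 2 at 100 ± 7 days (Table 2-3), 30.4375 days per month (SAP Section 8).

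- BV alone, no delays: last dose at 15 × 21 = 315 days; 315 + 100 = 415 days; 415 / 30.4375 = 13.6 months (13.4 to 13.9 with the ± 7 days).
- Nivolumab stopped in complete response at 2 years: (730.5 + 100) / 30.4375 = 27.3 months. Otherwise there is no cap.

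Section 3.2 cites for BV: "Longer follow up showed that the median overall survival (OS) and median PFS were 40.5 months". The BV-alone window covers about a third of that (13.6 / 40.5 = 0.34).

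**2. Size of the bias if the rule applies to everyone from randomization**

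From Section 3.2: median PFS 5.6 or 9.3 months, median OS 40.5 months. Assumed, not in the documents: exponential times; a share d of PFS events that are deaths (0, 5 or 10%); a constant death hazard μ after progression, solved so that median OS is 40.5 months. With λ = ln 2 / median PFS:

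S(t) = exp(−λt) + (1 − d) λ [exp(−μt) − exp(−λt)] / (λ − μ)

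Example: λ = ln 2 / 9.3 = 0.0745, d = 0.05, μ = 0.0249 gives S(12) = 0.409 + 0.95 × 0.0745 × (0.742 − 0.409) / 0.0496 = 0.884.

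The Kaplan-Meier limit comes from 400,000 simulated participants censored 100 days after progression. At 12 months the BV cap does not yet bind, so that column serves both treatment durations. The 24-month column is for an arm treated to progression with the same disease course.

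| Median PFS | d | 12 months: KM / true | Gap, points | 24 months: KM / true | Gap, points |
|---|---|---|---|---|---|
| 5.6 | 0% | 0.928 / 0.886 | 4.2 | 0.851 / 0.708 | 14.3 |
| 5.6 | 5% | 0.886 / 0.860 | 2.6 | 0.780 / 0.692 | 8.8 |
| 5.6 | 10% | 0.846 / 0.834 | 1.2 | 0.711 / 0.676 | 3.5 |
| 9.3 | 0% | 0.943 / 0.902 | 4.1 | 0.882 / 0.727 | 15.5 |
| 9.3 | 5% | 0.914 / 0.884 | 3.0 | 0.830 / 0.714 | 11.6 |
| 9.3 | 10% | 0.886 / 0.865 | 2.1 | 0.782 / 0.700 | 8.2 |

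Putting the last dose on the 21-day schedule adds at most about 1 point. Giving the combination arm a PFS hazard ratio of 0.62, 60% complete response with a stop at 24 months, and d = 5% (all assumed) yields 0.891 against 0.784 at 24 months, a gap of 10.7 points.

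**3. What shrinks it**

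- If participants already off treatment were followed to the revision date of 08-Jan-2020 (uniform entry assumed), the gap is about 0.1 to 0.6 points at 12 months in both arms. At 24 months it is 1.3 to 4.6 points in the combination arm.
- If progression leaves the death hazard unchanged, the estimate equals the truth (0.815 / 0.815 at 12 months, 0.663 / 0.663 at 24).

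**4. What 23 participants can show**

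With 12 per arm (8,000 runs, median PFS 9.3 months in the BV arm, d = 5%), the 12-month BV estimate has a standard deviation of 9 points. The BV arm has about 0.9 observed deaths, and its median is reached in 0.3% of runs.

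**5. Truncation versus selection in the BV arm**

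The share progression-free at dose 16 is 2^(−10.35/5.6) = 28% to 2^(−10.35/9.3) = 46%, where 10.35 = 315 / 30.4375 months. These participants are cut off without having progressed, so truncation is the larger problem in this arm.

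**The case against.** The strongest reply is that Section 10 already makes the planned analyses conditional and abandons inference, so the OS curve is no longer a firm commitment. That stands in part: no false-positive OS claim can follow if Section 10 is observed. But the clause gives no criterion for what is appropriate, and the SAP it points to still contains the full OS comparison. The SAP's own check, that minimum follow-up must reach a timepoint before a rate is shown, does not help. Section 7.5.3.1 measures it from the last randomization to the clinical cut-off, not by how long vital status was collected.

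A reader might infer that the curve will be about 15 points too high at 24 months and that nobody in the BV arm is at risk after 13.6 months. The documents do not support either as a general statement. The 15-point figure needs no deaths before progression and the rule applied to everyone from randomization. The protocol dates from 22-Feb-2017 and the revision from 08-Jan-2020, so some participants may have longer follow-up; the documents do not say. The 13.6 months excludes dose delays, which the protocol permits.

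Two further points stand. Random error with 23 participants exceeds any 12-month bias found. The 4-year text in Section 5.1 is leftover wording, since a dated paragraph in the same section states the stop rule.

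**Conclusion.** The concern holds in a limited form and should be fixed. The stop rule and the retained OS analysis do not fit together. For BV-alone participants under the rule and without delays, the curve ends near 13.6 months and the median is practically not estimable.

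The upward bias is conditional. It requires a higher death hazard after progression, which the documents support only qualitatively: the Introduction describes a very poor outlook after post-transplant relapse. Given that, it is about 1 to 5 points at 12 months and about 4 to 15 points at 24 months in an arm treated to progression, depending on the share of PFS events that are deaths. It falls to about 0.1 to 0.6 and 1 to 5 points if earlier participants were followed to the revision.

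The consequence is a misleading descriptive estimate and an OS objective that cannot be answered. It is not a false test result, and no stated decision rests on OS.

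**What to change.** - **Protocol Table 4-1 and Section 10.3.1 (and the matching synopsis text):** replace the OS curve and median with deaths and person-time from randomization to Follow-up Visit 2, by arm. Add a listing of any longer survival data collected before the revision. State that OS cannot be compared between arms.
- **SAP Section 7.5.2.3:** remove the OS log-rank test, hazard ratio and survival rates. The hazard ratio and rates appear only in the SAP, not in Protocol Section 10.3.1.
- **Leftover text:** reconcile the survival follow-up wording in the synopsis, Protocol Section 5.1, and SAP Sections 1 and 2.1 with the stop rule.

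If OS is to be kept, the alternative is one vital-status check of all participants at a common cut-off date. With complete ascertainment this removes the treatment-linked censoring. In the simulation, a 36-month cut-off returns the true BV curve (0.883, 0.712 and 0.553 at 12, 24 and 36 months) and raises expected BV deaths from about 0.9 to 5.4 of 12. A reader might take Sections 8.2 and 8.3 as already allowing this. They cover vital status where it is being measured and participants lost to follow-up, not contact after the study has ended. The check would need a protocol amendment with IRB/IEC approval, and consent withdrawal and loss to follow-up would limit it.

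Cost of the main fix: wording changes in two documents, and the loss of an OS curve and median that would be truncated and hard to interpret.

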**Table 2-3: Procedural Outline after the Treatment Period (CA209812) - Follow Up**

Procedure	X, Follow-Up, Visits 1 and 2 a	Notes
Subsequent anti-lymphoma therapies	X	It can be accomplished by visit or phone contact to assess subsequent anti-cancer therapy. Per Revised Protocol 01, stop after safety Follow-up Visit 2.
Post-nivolumab stem cell transplant follow-up (if applicable)	X	Completion of associated eCRF page. Per Revised Protocol 01, stop after safety Follow-up Visit 2.
GVHD Assessments	X	Only for participants who discontinued study therapy by proceeding to allogeneic SCT. See Section 9 and Appendix 9 . Per Revised Protocol 01, stop after safety Follow-up Visit 2.

a X, Follow-up visit 01 occurs 35 days ± 7 days from last dose and Follow-up visit 02 occurs 100 days ± 7 days from the last dose.

b Should a participant have a contraindication for CT IV contrast, a non-contrast CT of the chest and a contrast enhanced MRI of the abdomen and pelvis may be obtained. CTs and MRIs should be acquired with a slice thickness of 5 mm or less with no gap (contiguous).

[figure not shown]
### 3 INTRODUCTION

[figure not shown]
This study strives to improve disease control while minimizing treatment burden by incorporating two novel agents, nivolumab and brentuximab vedotin (BV), as salvage therapy in patients with relapsed Hodgkin Lymphoma (HL). The study targets patients who have relapsed after autologous stem cell transplant (ASCT) or are ineligible for ASCT.

Hodgkin lymphoma is a lymphoid malignancy characterized by the presence of multinucleated Reed-Sternberg cells, which are generally accepted to be of B-cell origin and usually account for only 1% to 10% of the cells in the tumor tissue. The majority of cells in HL tumor tissue are a mixed infiltrate of various lymphoid cells, including regulatory T-cells and macrophages. The updated 2008 WHO classification recognizes two histologic groups: nodular lymphocyte predominant, which accounts for about 5% of all HL cases, and “classical” HL (cHL) which accounts for the remainder.

In the totality of cancer epidemiology, HL represents a small percentage of all patients diagnosed with malignancy, yet it affects many considered as young adults. Approximately 8,500 new cases of HL are estimated to be diagnosed in the US in 2016 and more than 1,100 deaths from HL are expected. The prevalence of HL in the US in 2013 was estimated to be 193,545. The median age of diagnosis of HL in the US is 38 years; there is a bimodal age-specific incidence pattern, in which the incidence is highest between 15 and 34 years, declines between ages 35 and 54, and increases again after 55 years.

Improvements in the use of combined chemotherapy and radiotherapy in advanced stage newly diagnosed cHL have resulted in durable remission rates of approximately 60% to 80%. However, the remaining approximately 30% of patients will either relapse or have primary refractory disease. Failure to achieve complete response (CR) at the end of first-line therapy is considered as treatment failure. Salvage multi-agent chemotherapy, followed by ASCT, can only provide long-term disease control in approximately half of the patients with relapsed or refractory disease but at the price of additional acute and long-term toxicity. Patients who relapse after ASCT have an extremely poor prognosis and constitute a group with high unmet medical need.

### **3.2 Background**

[figure not shown]
High-dose chemotherapy with ASCT remains the optimal option to achieve a durable remission in patients with HL who have relapsed or are refractory to the standard frontline combination chemotherapy. Furthermore with ASCT approximately 50% of the patients are cured. Unfortunately, the remaining 50% of ASCT patients do not experience long-term disease control with median overall survival of approximately 27 months. In particular, the prognosis remains exceedingly poor for patients who experience relapse or progressive HL within one year after ASCT where the median survival time is approximately 1.2 years. Several small clinical studies

have examined various agents in the ASCT relapsed HL population with uniformly poor results. Therefore, the therapeutic options for these patients remain very limited. This underscores the need for more effective regimens for the treatment of relapsed, refractory HL.

Brentuximab vedotin is approved for patients who have progressed after ASCT or after failure of at least two prior multi-agent chemotherapy regimens in patients who are not ASCT candidates. In a pivotal phase 2 study of 102 patients with relapsed or refractory HL following ASCT, treatment with BV 1.8 mg/kg every 3 weeks resulted in an objective response rate (ORR) of 75% (95% CI: 64.9, 82.6). The CR rate was 34% (95% CI: 25.2, 44.4) and the median progression-free survival (PFS) for all patients on study was 5.6 months (95% CI: 5.0, 9.0). Longer follow up showed that the median overall survival (OS) and median PFS were 40.5 months (95% CI: 28.7, 61.9) and 9.3 months (95% CI: 7.1, 12.2), respectively. The estimated 5-year OS and PFS rates were 41% (95% CI: 31, 51) and 22% (95% CI: 13, 31), respectively. It should also be noted that BV is effective at the time of retreatment. Brentuximab vedotin is currently being developed by Seattle Genetics for the treatment of hematological malignancies.

Nivolumab has demonstrated promising activity as single agent in relapsed HL.

[REDACTED]

Brentuximab vedotin and nivolumab have demonstrated promising single-agent activity in HL. Additionally, both drugs work through distinct mechanisms of action. Given that both agents have demonstrated significant activity in HL, combination therapy could potentially be more effective in the salvage treatment setting than administration of either agent alone. Moreover, both agents are well tolerated, have few overlapping toxicities, and can be infused in the outpatient setting.

### **3.2.1 Nivolumab Mechanism of Action**

Cancer immunotherapy rests on the premise that tumors can be recognized as foreign rather than as self and can be effectively attacked by an activated immune system. An effective immune response in this setting is thought to rely on immune surveillance of tumor antigens expressed on cancer cells that ultimately results in an adaptive immune response and cancer cell death. Meanwhile, tumor progression may depend upon acquisition of traits that allow cancer cells to evade immunosurveillance and escape effective innate and adaptive immune responses. Current immunotherapy efforts attempt to break the apparent tolerance of the immune system to tumor cells and antigens by either introducing cancer antigens by therapeutic vaccination or by modulating regulatory checkpoints of the immune system. T-cell stimulation is a complex process involving the integration of numerous positive as well as negative co-stimulatory signals in addition to antigen recognition by the T-cell receptor. Collectively, these signals govern the balance between T-cell activation and tolerance.

PD-1 is a member of the CD28 family of T-cell co-stimulatory receptors that also includes CD28, CTLA 4, ICOS, and BTLA. PD-1 signaling has been shown to inhibit CD28-mediated upregulation of IL-2, IL-10, IL-13, interferon- $\gamma$  (IFN- $\gamma$ ) and Bcl-xL. PD-1 expression also been noted to inhibit T cell activation, and expansion of previously activated cells. Evidence for a negative regulatory role of PD-1 comes from studies of PD-1 deficient mice, which develop a variety of autoimmune phenotypes. These results suggest that PD-1 blockade has the potential to activate anti-self T-cell responses, but these responses are variable and dependent upon various host genetic factors. Thus, PD-1 deficiency or inhibition is not accompanied by a universal loss of tolerance to self-antigens.

In vitro, nivolumab (BMS-936558) binds to PD-1 with high affinity (EC50: 0.39-2.62 nM), and inhibits the binding of PD-1 to its ligands PD-L1 and PD-L2 (IC50:  $\pm$  1 nM). Nivolumab binds specifically to PD-1 and not to related members of the CD28 family such as CD28, ICOS, CTLA-4 and BTLA. Blockade of the PD-1 pathway by nivolumab results in a reproducible enhancement of both proliferation and IFN- $\gamma$  release in the mixed lymphocyte reaction. Using a cytomegalovirus (CMV) re-stimulation assay with human PBMC, the effect of nivolumab on antigen specific recall response indicates that nivolumab augmented IFN- $\gamma$  secretion from CMV specific memory T cells in a dose-dependent manner versus isotype-matched control. In vivo blockade of PD-1 by a murine analog of nivolumab enhances the anti-tumor immune response and result in tumor rejection in several immunocompetent mouse tumor models (MC38, SA1/N, and PAN02).

